
Methodology: This is a multi-center, randomized, double-blind, placebo-controlled crossover study to evaluate the effect of the isoflavone genistein on the short-term untoward effects of myelosuppressive chemotherapy used to treat pediatric cancers. Newly diagnosed cancer patients aged 1 - 21 years will be registered to the study and informed consent will be obtained prior to any study-related procedures. Stratification will be based on length of chemotherapy cycles: 14 days or 21 days. Subjects will be randomized 1:1 to one of two schedules within each stratum:
 
Arm A: Subjects will receive genistein daily throughout chemotherapy Cycles 1 and 2, and placebo during chemotherapy Cycles 3 and 4
 
Arm B: Subjects will receive placebo daily throughout chemotherapy Cycles 1 and 2, and genistein during chemotherapy Cycles 3 and 4
 
The safety and efficacy of genistein will be assessed during each cycle through clinical laboratory tests, cytokine panels, and physical exams. Study supplement compliance will be monitored by use of a subject diary, drug reconciliation, and serum isoflavone levels. Adverse events will be monitored starting on Cycle 1 Day 1 through 30 days following the last day of study supplementation (genistein/placebo). Serious adverse events will be collected through 6 months post-study intervention.
	
Number of subjects (planned): Up to 50 subjects will be accrued to obtain 44 eligible subjects.	

Main Eligibility Requirements:
 
Inclusion criteria:
 
 New diagnosis of a solid tumor or lymphoma, with histologic verification of malignancy Age 1 - 21 years at the time of diagnosis Able to tolerate enteral medication administration Performance score minimum requirement ≥ 50 on Karnofsky/Lansky scale Planned chemotherapy regimen involves at least four consecutive cycles of chemotherapy that is known to be myelosuppressive 
Exclusion criteria:
 
 Known allergy to soy or any soy-based food or supplement Pre-existing neutropenia or neutrophil qualitative or quantitative disorder Pre-existing cytopenia or bone marrow failure syndrome Subject will not receive myelosuppressive chemotherapy Current acute or chronic leukemia diagnosis Enrolled on another therapeutic or supportive care clinical trial within the last 30 days Secondary malignancy 	

Investigational intervention:

- Genistein: 30 mg/day, oral tablets
- Placebo: oral tablets

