9.1 Definitions

9.1.1 Adverse Event [72]

An adverse event is any untoward medical occurrence in a subject who has received an investigational intervention, whether or not related to the investigational intervention(s). Medical conditions present before starting the investigational intervention (pre-existing conditions) will be considered AEs only if they worsen after starting the study supplement ([Sections 6.3](#) and [9.1.6](#)). AEs include unfavorable, harmful or pathological changes in the general condition of a subject; subjective or objective symptoms (spontaneously offered by the subject and/or observed by the Investigator or the study nurse); intercurrent events or exacerbation of pre-existing diseases which occurred after the administration of the study supplement; clinically significant changes in laboratory abnormalities; or any undesirable and unintended effect of research occurring in human subjects as a result of the collection of identifiable, private information for research purposes.

Only clinically significant AEs will be reported on this study. Reporting will include, at minimum, the dates of onset and resolution, severity, attribution to study intervention, expectedness, seriousness, and treatment (medication, transfusion, procedure, other, or none). AEs should be reported as diagnoses, when possible.

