9.2.3.3 Reporting to the FDA

The Study Chair or designee is responsible for providing safety updates to the FDA per the following guidelines. The reporting times refer to the time the study team received knowledge of the AE.

Table 9. FDA Reporting Requirements

UVa PI HELD IND			
Type of Event	To whom will it be reported:	Time Frame for Reporting	How reported?
Life-threatening and/or fatal unexpected events related or possibly related to the use of the investigational agent.*	FDA	Within 7 calendar days of the study team learning of the event	Form FDA 3500A (MedWatch) or narrative
Serious, unexpected and related or possibly related AEs*	FDA	Within 15 calendar days after the study team receives knowledge of the event	Form FDA 3500A (MedWatch) or narrative
All AEs	FDA	Annually	IND annual report

*Applies to AEs/SAEs not identified in [Appendix C](#)

Certain anticipated SAEs will not be reported individually to the FDA in an expedited fashion due to their frequency in the study population independent of study supplement exposure. The events listed in [Appendix C](#) are common in patients receiving the chemotherapeutic agents listed in [Section 3.1](#) and so will instead be reported in aggregate to the FDA using an IND safety report should analysis indicate that the toxicities are occurring more frequently in patients taking genistein.

The Study Chair may also choose to refrain from single-event IND safety reporting should an AE/SAE be related to the subject’s underlying disease. These events are not included in [Appendix C](#) due to the wide range of cancers that may participate in this study. As above, such AE/SAEs will be reported using an IND safety report should aggregate analysis demonstrate increased toxicity associated with genistein treatment.

Single-event IND safety reports submitted to the FDA will be blinded, per permission granted by the agency on 19May2017.

Annual reports to the FDA will include AEs and SAEs collected as described in [Section 9.2.1](#), with the exception of target AEs collected solely for the purposes endpoint analysis. Those target AEs are non-serious grades 1 and 2, any attribution to the study supplement, and non-serious grade 3 with an unrelated or unlikely relationship to the study supplement.

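### Section 9.2.3.3: the underlying-disease discretion can only act to delay FDA reports of serious, unexpected, possibly supplement-related events, fatal ones included, and it conflicts with Tables 9 and 10

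*Combined protocol and SAP*

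**What the plan says.** Table 9 in Section 9.2.3.3 has two expedited rows. The 7-day row covers "Life-threatening and/or fatal unexpected events related or possibly related to the use of the investigational agent". The 15-day row covers "Serious, unexpected and related or possibly related AEs". Both carry a footnote that begins "Applies to AEs/SAEs not identified in" and names Appendix C, a list fixed in advance of toxicities common with the chemotherapy agents. A third row sends all AEs to the FDA once a year.

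The text below the table adds a second exemption that is not in the footnote, for events attributed to the disease under treatment. The sentence granting it opens "The Study Chair may also choose to refrain from single-event IND safety reporting should an AE/SAE be related to". No list of such events is given, and the reason offered is "due to the wide range of cancers that may participate in this study". The stated fallback is that "such AE/SAEs will be reported using an IND safety report should aggregate analysis demonstrate increased toxicity associated with genistein treatment". For this exemption the section sets no limit on grade or outcome, no second reviewer, and no record of the decision.

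Table 10 in Section 9.2.3.4 requires an IND Safety Report to all research sites within 15 days for the class worded as in Table 9's 15-day row. It has no footnote and no exemption.

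**The concern.** An exemption for disease-related events reads as if it keeps background events out of the expedited stream. But Table 9 has already removed events judged unrelated or unlikely to be related to the supplement. What is left for the discretion is the group in which an investigator thought the supplement might have contributed and the disease is a competing explanation. In that group a single case report carries the most information, because attribution is uncertain and few such events are likely.

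The protocol gives reasons for care. Section 1.3 describes the safety data for soy isoflavones in pediatric cancer patients as limited, and Section 5.1.7 says that genistein may worsen estrogen-sensitive conditions. At stake is whether the FDA learns of a fatal or life-threatening, possibly related event on the 7-day or 15-day clock or only later, and whether the FDA and the sites receive the same information at the same time.

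**Working it through.** The plan gives no figure to reproduce. The check is mainly logical, with one small calculation on the fallback.

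**Step 1. Which events can the discretion affect?** An event reaches an expedited row of Table 9 only if all of these hold:
- it is serious (Section 9.1.9, which includes fatal and life-threatening events);
- it is unexpected;
- it is related or possibly related to the supplement (in Section 9.1.10: possible, probable or definite);
- it is not in Appendix C (footnote).

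Taking each kind of disease-related event in turn:
- Non-serious: never in an expedited row, so the discretion changes nothing.
- Expected: the same.
- Unlikely or unrelated: the same.
- In Appendix C: already exempt.
- Serious, unexpected, at least possibly related, outside Appendix C: reportable under Table 9 unless the Study Chair declines.

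Only the last kind is affected. If disease-related were read as meaning not related to the supplement, the sentence would have no effect, since such events are already outside Table 9.

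**Step 2. How does it fit with the other reporting rules?**
- Table 9 footnote: one exemption (Appendix C). Text of 9.2.3.3: two.
- Table 10: the same class goes to all sites in 15 days with no exemption. Its package calls for a copy of the MedWatch form or a narrative, the same formats that Table 9 names for the FDA report. If the discretion is used, sites are due an IND Safety Report that the FDA has not received at that time.

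**Step 3. What still happens to a withheld event?**
- Every SAE is entered in OnCore within 24 hours, whatever its grade or attribution (Tables 5 and 6).
- At the UVa site, an internal serious unexpected AE goes to the IRB within 7 days (Table 7).
- The DSMC reviews AEs monthly, in blinded format (Section 10.2). The Study Chair and Study Statistician review SAEs at least every six months (Section 10.3).
- The FDA receives the event in the annual report. The only exceptions there are certain non-serious target AEs, so a serious event is always included.

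The FDA report therefore moves from 7 or 15 days to the next annual report, at most about a year, unless the aggregate analysis brings it forward.

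**Step 4. Would the aggregate analysis bring it forward?** The documents state no method, threshold or schedule. As an illustration only, assume equal genistein and placebo exposure and a one-sided 5% exact binomial test. If all k events of one type fall in genistein cycles, p = 0.5^k:
- k = 1: 0.5
- k = 2: 0.25
- k = 3: 0.125
- k = 4: 0.0625
- k = 5: 0.031

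Under these assumptions at least five events of one type, with none under placebo, are needed before the test is positive. One rare event would not trigger it.

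**The case against.** The strongest reply is that little is lost. The channels in Step 3 carry no such exemption, so the Study Chair's discretion covers the single-event FDA report and nothing else. Section 9.1.7 lets the expectedness of SAEs take account of the underlying disease, so many disease complications may already count as expected and fall outside Table 9. The estrogen concern is partly met by exclusion criterion 15. The discretion is an explicit exception in the same section, and it may rest on agency correspondence that is not in the documents; the one permission cited, from 2017, concerns blinded reports. All of this stands, and it limits the size of the point. It does not explain why an event judged possibly related, perhaps fatal, should leave the 7-day or 15-day clock at one person's choice, or why Tables 9 and 10 say something different from the text.

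Three stronger readings are tempting, and the documents do not support them.
- **The FDA might never learn of a fatal case.** The annual report includes it.
- **Withheld cases could not be found later.** Section 9.1.1 lists "severity, attribution to study intervention, expectedness, seriousness, and treatment" among the minimum items and has no disease-attribution item. But that list is a minimum, Sections 6.3 and 6.4 capture progression or relapse, secondary malignancy and death separately with dates and descriptions, and SAEs are in OnCore with supplement attribution. What is missing is a record of the decision to withhold.
- **After Cycle 4 an aggregate comparison has no contrast, because both arms have by then been assigned two genistein cycles.** The arms still differ in recency. Arm B has just finished genistein, while Arm A stopped about two cycles earlier (2 × 14 = 28 or 2 × 21 = 42 days). Early discontinuation also leaves exposures unequal. The contrast is weaker, not absent.

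**Conclusion.** The point holds as a defect in the reporting rules. As written, the discretion takes effect only on serious, unexpected, at least possibly supplement-related events outside Appendix C, with no exception for fatal or life-threatening outcomes. It contradicts the Table 9 footnote and is not matched in Table 10. The consequence is a later FDA report, and a period in which sites may hold an IND Safety Report that the FDA does not.

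That the discretion falls wholly on supplement-related events follows from how Table 9 is built. It says nothing about how many events are involved. That number is not given; it is probably small, and smaller still if Section 9.1.7 governs expectedness for Table 9. The view that the aggregate fallback would not respond to a single rare event rests on the assumed test and equal exposure in Step 4. No view is taken on what IND regulation requires, since that lies outside the documents. A correction is worth making because it concerns patient safety and costs little.

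**What to change.** In Section 9.2.3.3, state that an unexpected serious event judged possibly, probably or definitely related to the supplement is reported under Table 9 even when the underlying disease is an alternative cause. If the discretion is kept, state at minimum that it never applies to fatal or life-threatening events. Neither option needs a list of disease events, so the protocol's reason for leaving them out of Appendix C is respected.

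Make the Table 9 footnote and Table 10 agree with the text. Table 10 should say whether any exemption, Appendix C included, applies to reports to sites.

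If any discretion remains, record each decision to withhold a single-event report, so that those events can be included in the aggregate analysis. The Appendix C exemption itself needs no change, either during treatment or in follow-up.

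The cost is one revised paragraph, matching wording in two tables, one item to record, and probably a few more single-event reports.

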9.2.3.4 Reporting to Participating Sites

The Study Chair or designee is responsible for providing safety updates to all participating sites per the following guidelines:

Table 10. Required Reporting to Participating Sites

UVa PI of MULTI-SITE TRIAL			
Type of Event	To whom will it be reported:	Time Frame for Reporting	How reported?
Serious, unexpected and related or possibly related AEs	All Research Sites	Within 15 calendar days after the Study Chair receives knowledge of the event	IND Safety Report (Cover letter, copy of MedWatch or narrative)
Unanticipated Problem	All Research Sites	Within 15 calendar days from the time the Study Chair receives knowledge of the event.	Letter to Site PIs, Copy of MedWatch or narrative

10 DATA SAFETY MONITORING PLAN

The Study Chair will provide continuous monitoring of subject safety in this trial with periodic reporting to the UVa Data Safety Monitoring Committee (DSMC).

10.1 Data Collection/CRF Completion

All data must be entered into OnCore in accordance the University of Virginia Cancer Center OnCore standard operating procedure (SOP), which can be found on the OnCore Resources page (see the OnCore Help tab). AEs must be entered into OnCore as described in [Section 9.2](#) and in the Procedure Manual. All other study specific data must be entered into OnCore in the timeframes specified in the SOP. Sample CRFs are available in the Procedure Manual appendices.

10.2 UVa Cancer Center Data Safety Monitoring Committee

The UVa Cancer Center (CC) Data and Safety Monitoring Committee (DSMC) will provide oversight of the conduct of this study. The CC DSMC will report to the UVa Protocol Review Committee (PRC). These reports will also be provided to participating sites for submission to their IRBs.

The DSMC will review the following data in blinded format:

- All AEs
- Audit results
- Application of study designed stopping/decision rules
- Whether the study accrual pattern warrants continuation/action
- Protocol violations

The CC DSMC will meet every month for aggregate review of AE data. Tracking reports of the meetings are available to the Study Chair for review. Issues of immediate concern by the DSMC are brought to the attention of the Study Chair (and if appropriate to the PRC and IRB) and a formal response from the Study Chair is requested. Per the CC NIH-approved institutional plan this study will be audited approximately every 6 or 12 months.

10.3 Review of Adverse Events by the Study Team

Individual AEs will be reviewed by the treating physician and/or principal investigator, and the clinical research coordinator(s) (CRC). Additional staff on the research team may also review AEs.

SAEs will be reviewed by the Study Chair and Study Statistician at least once every six months after the first subject's first dose with study supplement. Those present at the meeting may include the Study Chair, PIs at other sites, sub-investigators, protocol

development staff, biostatisticians, research nurses, research coordinators, laboratory specialists, and laboratory research managers. These meetings also include the review of individual participants to assess whether they are protocol candidates, whether AEs warrant discontinuation, and whether the existing protocol should be continued, amended, or closed.

DRAFT

11 STUDY MANAGEMENT

11.1 IRB Approval and Consent

It is expected that the IRB will have the proper representation and function in accordance with federally mandated regulations. Each site's IRB must approve the consent form(s) and protocol. All initial and amendment approvals, annual renewals, and IRB-stamped consent forms must be submitted to the Study Manager (Procedure Manual).

[Section 4.3](#) outlines expectations for properly obtaining and documenting informed consent.

11.2 Adherence to the Protocol

Except for an emergency situation in which proper care for the protection, safety, and well-being of the study subject requires alternative treatment, the study shall be conducted exactly as described in the approved protocol. The UVa IRB-HSR will approve all aspects of this study, including the clinical trial protocol, informed consent documents, and subject materials. Modifications to the protocol or consent form will be reviewed and approved by the UVa IRB-HSR prior to implementation, except when necessary to eliminate apparent immediate hazards to the study participants. The study will undergo continuing IRB review based on the level of risk as assessed by the IRB. This review will take place no less than annually. Participating sites will be responsible for ensuring their consent forms are written in accord with 21 CFR 50.

Affiliate sites must submit this study for the review of their local site IRBs in accordance with local policies. At a minimum, all consent forms, the protocol (all versions from the time of affiliate start-up), annual renewals, and study closure must be approved by the site IRB. See the Procedure Manual for further details.

11.2.1 Emergency Modifications

Investigators may implement a deviation from, or a change of, the protocol to eliminate an immediate hazard(s) to trial subjects without prior IRB approval/favorable opinion, if permitted by the site's IRB.

For any such emergency modification implemented at UVa, an IRB modification form must be completed by study personnel within five (5) business days of making the change.

11.2.2 Protocol Deviations/Violations

Protocol Deviations: A protocol deviation is any unplanned variance from an IRB approved protocol that:

- Is generally noted or recognized after it occurs
- Has no substantive effect on the risks to research participants

- Has no substantive effect on the scientific integrity of the research plan or the value of the data collected
- Did not result from willful or knowing misconduct on the part of the investigator(s).

Study personnel will record the deviation, and report to the Sponsor or DSMC in accordance with their policies. Deviations must be summarized and reported to the site IRB at the time of continuing review or according to site IRB's policy.

Protocol Violations: An unplanned protocol variance is considered a violation if the variance:

- Has harmed or increased the risk of harm to one or more research participants.
- Has damaged the scientific integrity of the data collected for the study.
- Results from willful or knowing misconduct on the part of the investigator(s).
- Demonstrates serious or continuing noncompliance with federal regulations, State laws, or institutional policies.

Violations must be reported by study personnel to the site IRB in accordance with the site IRB's policy and to the Sponsor as outlined in the Procedure Manual.

11.3 Record Retention

Study documentation includes all CRFs, data correction forms or queries, source documents, Sponsor-Investigator correspondence, monitoring logs/letters, and regulatory documents (e.g. protocol and amendments, IRB correspondence and approvals/acknowledgements, signed subject consent forms).

Source documents include all recordings of observations or notations of clinical activities and all reports and records necessary for the evaluation and reconstruction of the clinical research study.

Government agency regulations and directives require that all study documentation pertaining to the conduct of a clinical trial must be retained by the study investigator. In the case of a study with a drug seeking regulatory approval and marketing, these documents shall be retained for at least two years after the last approval of marketing application in an International Conference on Harmonization (ICH) region. In all other cases, study documents must be kept on file until six years after the completion and final study report of this investigational study. Completion is defined as study closure through the UVa IRB-HSR.

11.4 Obligations of Investigators

The PI is responsible for the conduct of the clinical trial at their site in accordance with Title 21 of the Code of Federal Regulations, all applicable local regulatory laws and regulations and/or the Declaration of Helsinki. The PI is responsible for personally

overseeing the treatment of all study subjects at his or her site and must assure that all study site personnel, including sub-investigators and other study staff members, adhere to the study protocol and all FDA/GCP/NCI regulations and guidelines regarding clinical trials both during and after study completion. It is the responsibility of the PI to ensure that all study site personnel are aware that the study protocol and all data generated is confidential and not disclosed to third parties (with the exception of local and national regulatory bodies which require access for oversight purposes).

The PI at each institution or site will be responsible for assuring that all the required data will be collected and entered onto the CRFs. Periodically, monitoring visits will be conducted and the PI will provide access to his or her original records to permit verification of proper entry of data. At the completion of the study, all CRFs will be reviewed by the PI and will require his or her final signature to verify the accuracy of the data.

DRAFT

